DRUG USE INVESTIGATION FOR HIV INFECTION PATIENTS OF MARAVIROC

- HRD Joint Survey -

STATISTICAL ANALYSIS PLAN

CELSENTRI Tablets 150 mg Statistical Analysis Plan

Outsourced by
Product name
Pregnant Women
Prepared by

ViiV Healthcare K.K.
CELSENTRI Tablets 150 mg Drug Use Survey, Special Drug Use Survey for
CMIC-PMS Co., Ltd. PPD

<General Definitions>

Re-examination period	
Number of report	Survey period
1st	2008/12/25 (H20) - 2009/2/5
2nd	2/6/2009 (H21) - 8/5/2009
3rd	8/6/2009 (H21) - 2/5/2010
4th	2/6/2010 (H22) - 8/5/2010
5th	8/6/2010 (H22) - 8/5/2011
6th	8/6/2011 (H23) - 8/5/2012
7th	8/6/2012 (H24) - 8/5/2013
8th	8/6/2013 (H25) - 8/5/2014
9th	8/6/2014 (H26) - 8/5/2015
10th	8/6/2015 (H27) - 8/5/2016
11th	8/6/2016 (H28) - 8/5/2017
12th	8/6/2017 (H29) - 8/5/2018
13th	8/6/2018 (H30) - 12/24/2018
Re-examination	12/25/2008 (H20) - 12/24/2018
Date conversion	
When you calculate dates for aggregation, make the following replacement: Replace the date “AA=early in the month” with 05, “BB=middle of the month” with 15, “CC=late in the month” with 25, and “DD=around” with 01. Replace “20EEEEEE=continued” with “the outcome confirmation date of the patient”. If nothing is provided, enter “entry date”. The new survey does not have entries of 20EEEEEE, but enter 20EEEEEE for continued administration if “entry date” is found. When you need to replace any inappropriate date (such as Day 00), add the following process: When the date in “first administration date” is not appropriate as a date, choose the final date of the month. When the month and date in “first administration date” are not appropriate as a date, enter “1231”. When the date in “final administration date” is not appropriate as a date, enter “01”. When the date in “onset date of adverse event” is not appropriate, enter “01”. When the date in “laboratory test date” is “00” or “99”, enter “01”. Only a date after the approval date (=December 25, 2008) should be used for CELSENTRI Tablets (when the first administration date comes before the approval date, replace it with the approval date).

Date unit	A week has 7 days, a month has 30 days, and 1 year has 365 days.
Prior to administration	It should be within 30 days prior to the first administration of CELSENTRI Tablets and be the closest date to the first administration date (the administration date is also included).
Displayed digit	Decimal numbers should be rounded to the second decimal place.

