Missing data	When aggregating “unknown” and “not provided”, count them collectively as “unknown/not provided”. Of note, separate “unknown” and “not provided” for “medical history” and “allergy history”.

MedDRA	Use MedDRA/J Version 21.0. Count PTs for aggregation and use primary for SOC.
Adverse events	Adverse events for which the “relationship” column with CELSENTRI Tablets is not checked or “no relationship” is checked among the events that occurred on or after the first administration date of the drug, plus, the adverse reactions that are defined below. But the decision is based on the ViiV Healthcare’s company assessment. Of note, they also include the event for which you can’t decide whether it occurred on the first administration date of CELSENTRI Tablets because of unknown date even after <General Definitions> “Date conversion” resulting from its inarticulate onset date. Overlapped events with the same PT in a patient should be counted as one event in accordance with <General Definitions> “Integration process”.
Adverse reactions	The events for which the relationship with CELSENTRI Tablets cannot be ruled out. The decision is based on ViiV Healthcare K.K.’s company assessment.
Serious adverse events	“Serious” events in the seriousness criteria among the above “adverse events”. The decision is based on ViiV Healthcare K.K.’s company assessment.
Co-administration	Co-administration refers to a drug concomitantly used for at least a day. Of note, if only one date is overlapped when two anti-HIV drugs are used on the same day (as the first administration for one and the final administration for the other), it should be regarded as “replacement” and not counted as a concomitant drug.
Integration process	Take the following integration process per PT.
	<When the events occurred on the same date>
[Seriousness]	Integrate into a more severe event.
[Relationship]	The same years: Integrate into the final year when the relationship was observed. Different years: Integrate into the final year.
[Outcome (outcome confirmation date)]	The same year: Death>Not recovered>Recovered with sequela>Unknown>Recovering>Recovered>Not provided Different years: Integrate into the final year.
	Of note, when the onset date is unknown or not provided, the event with the onset date should be selected.
	<When the events occurred on different dates>
[Onset date]	Select the initial onset date.
[Seriousness]	Integrate into a more severe event.

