[Relationship]	Integrate into the date of the “related” event.
[Outcome (outcome confirmation date)]	The same year: Death>Not recovered>Recovered with sequela>Unknown>Recovering>Recovered>Not provided Different years: Integrate into the final year.
	Of note, when the onset date is unknown or not provided, the event with the onset date should be selected.
	<Processing order> Process [1]: Events which occurred in the same year and on the same date Process [2]: Events which occurred in different years but on the same date Process [3] Events which occurred in the same year but on different dates Process [4] Events which occurred in different years and on different dates.
Test	Exclude “unknown”, “not provided” and “not assessable” from test. Do not conduct a test for the items with multiple answers. When χ^2 test is conducted and the degree of freedom (DF) is 1, conduct Fisher’s exact test as well for the item.

<Handling of items>

Number of sites for the survey	Department codes (per contract) are included in the DCF site code. Count the number of site as one.
Primary disease	Give priority to "1=HIV Infection" throughout a year. "AIDS" should be regarded as "HIV Infection" in "2. Others". Others should be "Others". [Stratification] HIV Infection, Others
Sex	Use the value in the CRF at the first administration of CELSENTRI Tablets. [Stratification] Men, Women
Presence/absence of pregnancy	Patients who receive CELSENTRI Tablets for at least one day during pregnancy (if the date of last menstrual period (LMP) is unknown after LMP, see Week 0 of pregnancy or later; if both are unknown, see the pregnancy diagnosis date or later) among the patients in "Sex:3" (Pregnancy: present). Include the cases with "Women" in "Sex". [Stratification] Absence, Presence, Unknown/not provided

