Age	Calculate the Western-style age as of the initial administration date of CELSENTRI Tablets based on the date of birth. Of note, if the description only includes the year for date of birth in a site, describe it as "January 1". If it only includes the year and the month, replace it with "the first date of the month". If a "period of age" or "age" is provided in the "date of birth" column, select the "period of age" or "age" provided in the CRF when the patient was started on CELSENTRI Tablets only after confirmation that it is the data for the applicable year. [Stratification] [1] ≤14 years old, ≥15 and ≤64 years old, ≥65 years old, unknown/not provided [2] ≤9 years old, ≥10 and ≤19 years old, ≥20 and ≤29 years old, ≥30 and ≤39 years old, ≥40 and ≤49 years old, ≥50 and ≤59 years old, ≥60 and ≤69 years old, ≥70 years old, unknown/not provided
Inpatient/outpatient classification	Use the value in the CRF at the first administration of CELSENTRI Tablets. [Stratification] inpatient, outpatient, inpatient
Treatment history for HIV infection	Use the value in the CRF at the first administration of CELSENTRI Tablets. However, if an anti-HIV drug is administered prior to the initiation of CELSENTRI Tablets, select "2=present". [Stratification] Absence, Presence, Unknown/not provided
Race	Use the value in the CRF at the first administration of CELSENTRI Tablets. [Stratification] Japanese, others, unknown/not provided
Route of infection	Use the value in the CRF at the first administration of CELSENTRI Tablets. <Multiple-answers are acceptable in this column> [Stratification] Blood product, Mother-to-child transmission, Medical accident, Sexual transmission, Others, Unknown/not provided
Duration of disease	Calculate the years from infection to the first administration date. Display the minimum and the maximum as well. [Stratification] ≤1 year, >1 year and ≤2 years, >2 years and ≤3 years, >3 years and ≤4 years, ≥5 years, unknown/not provided
Medical history	Use the value in the CRF at the first administration of CELSENTRI Tablets. If there is an event that both occurred and recovered before the first administration of CELSENTRI Tablets in the 'adverse event' column, regard it as "present". [Stratification] Absence, Presence, Unknown/not provided
Presence/absence of allergy	Use the presence/absence of allergy provided in the CRF at the first administration of CELSENTRI Tablets. [Stratification] Absence, Presence, Unknown/not provided

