Patient composition ratio	Display the number of patients and the patient composition ratio for the following patient background items. Follow the above <<Handling of Items>> for the definitions of each item per background. ◎ Displayed items: primary disease, sex, presence/absence of pregnancy, age, inpatient/outpatient classification, treatment history of HIV infection, race, route of transmission, duration of disease, medical history, allergy, complication, type of complication, renal disorder, liver disorder, the mean daily dose, administration period, administration period [cumulative], total dose, total dose [cumulative], continued/discontinued, concomitant drug, number of concomitant drugs, type of concomitant drugs, number of concomitant anti-HIV drugs, type of concomitant anti-HIV drugs, presence/absence of CYP3A inducer, presence/absence of haemophilia, haemophilia AB, CDC classification of severity prior to administration, tropism classification at the first administration, concomitant treatment, blood coagulation factor (all cases and the cases with haemophilia) Calculate the minimum and the maximum for age, duration of disease, the mean daily dose, administration period, total dose while calculate the mean and the standard deviation for age as well (Of note, as to the description age for example, calculate the age of a patient in his 30s will be calculated as 30 years old).
Line list (Basic patient-background data)	Retrieve the items provided in the mock-up from CELSENTRI-Tablets data base. Of note, display the calculated or edited values for the items with (calculate result) provided under the item name in the mock-up.
A list of the reasons why the tropism assay was not conducted	Pick up the patients who did not undergo the tropism assay and retrieve the reasons why the test was not conducted.
A list of the patient summary for the survey	Prepare the list based on the sheet “A list of the patient summary for the survey”. See “166272A1” and “166272B1” in the mock-up.

3) Table for “Patients in the safety analysis group”.

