*A list of adverse reactions per patient background, etc.	Prepare a list for adverse reactions in <General Definitions>. © Displayed items: No., patient registration number, age, pediatrics, the elderly, race, presence/absence of pregnancy, presence/absence of complications, haemophilia, renal disorder, hepatitis A, hepatitis B, hepatitis C, others, liver disorder, syphilis, others, presence/absence of haemophilia, presence/absence of liver disorder, presence/absence of renal disorder, name of complication, presence/absence of allergy, presence/absence of concomitant treatment, name of concomitant treatment, presence/absence of concomitant drugs, number of concomitant drugs, presence/absence of concomitant anti-HIV drugs, number of concomitant anti-HIV drugs, administration period, long-term administration, presence/absence of adverse events, presence/absence of adverse reactions, name of adverse reactions (PT), seriousness, outcome, days to the onset, relationship with CELSENTRI
Incidence of adverse reactions per patient background	Prepare a table of incidence of adverse reactions on the following patient-background items: Follow the above <<Handling of Items>> for the definitions of each item per background. © Displayed items: primary disease, sex, presence/absence of pregnancy, age, inpatient/outpatient classification, treatment history of HIV infection, race, route of transmission, duration of disease, medical history, allergy, complication, type of complication, renal disorder, liver disorder, the mean daily dose, administration period, administration period [cumulative], total dose, total dose [cumulative], continued/discontinued, concomitant drug, number of concomitant drugs, type of concomitant drugs, number of concomitant anti-HIV drugs, type of concomitant anti-HIV drugs, presence/absence of CYP3A inducer, presence/absence of haemophilia, haemophilia AB, CDC classification of severity prior to administration, tropism classification at the first administration, concomitant treatment, blood coagulation factor (all cases and the cases with haemophilia) Calculate the minimum and the maximum for age, duration of disease, the mean daily dose, administration period, total dose while calculate the

	mean and the standard deviation for age as well (Of note, as to the description age for example, calculate the age of a patient in his 30s will be calculated as 30 years old).

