Data on the incidence of adverse reactions per patient background	Display the incidence of adverse reactions per patient background for each patient.
A list of the onset status of adverse reactions/infections per patient background	Prepare a list of the onset status of adverse reactions/infections for each patient background item below. Follow ‘adverse reactions’ of <General Definitions> for the onset status of adverse reactions while follow the above <Handling of Items> for the definition of each patient-background item. © Displayed items: primary disease, sex, presence/absence of pregnancy, age, inpatient/outpatient classification, treatment history of HIV infection, race, route of transmission, duration of disease, medical history, allergy, complication, type of complication, renal disorder, liver disorder, the mean daily dose, administration period, administration period [cumulative], total dose, total dose [cumulative], continued/discontinued, concomitant drug, number of concomitant drugs, type of concomitant drugs, number of concomitant anti-HIV drugs, type of concomitant anti-HIV drugs, presence/absence of haemophilia, haemophilia AB, CDC classification of severity prior to administration, concomitant treatment, blood coagulation factor (all cases and the cases with haemophilia)
Number of days to administer until the day on which adverse reactions first occurred	Prepare a table by number of days ≤ 180 days, 180 days < ≤ 365 days, 365 days < ≤ 730 days, 730 days <
The incidence of adverse reactions per concomitant drug	Prepare a table of incidence of adverse reactions regarding concomitant drugs per drug code (the first 7 digits). Follow “Co-administration” of <General Definitions> for the definition of co-administration.
A table of patient numbers per concomitant drug	Prepare the patient registration numbers for each drug code (the first 7 digits) regarding concomitant drugs with and without patients with adverse reactions. Follow “Co-administration” of <General Definitions> for the definition of co-administration.
The incidence of adverse reactions per complication	Prepare a table of incidence of adverse reactions per PT regarding complications and other contents. The definition of complications is applied to the patients with “complications” of <Definitions of Items>.

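### Duration-of-disease strata have no row for known durations over 4 and under 5 years, and one efficacy split uses CYP3A inhibitors although the SAP defines only inducers

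*SAP*

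**What the plan says.** **Duration of disease.** The SAP (Handling of items, Duration of disease) gives this derivation: "Calculate the years from infection to the first administration date". The rows are ≤1, >1 to ≤2 and >2 to ≤3 years, and then ">3 years and ≤4 years, ≥5 years, unknown/not provided". General Definitions, Date unit, states: "A week has 7 days, a month has 30 days, and 1 year has 365 days". For unknown and not-provided entries, General Definitions, Missing data, says to "count them collectively as “unknown/not provided".

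The item is used in three outputs:
- table section 2, Patient composition ratio: "Display the number of patients and the patient composition ratio for the following patient background items";
- table section 3, incidence per patient background: "Prepare a table of incidence of adverse reactions on the following patient-background items";
- table section 3, onset status per patient background: "Prepare a list of the onset status of adverse reactions/infections for each patient background item below".

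The rule on tests in General Definitions is "Exclude “unknown”, “not provided” and “not assessable” from test". It also bars tests on multiple-answer items, and duration is not one of those.

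**CYP3A.** Handling of items defines one CYP3A item, use of a concomitant inducer, and refers to a sheet that lists inducers. The composition table and the adverse-reaction incidence table display inducer use. Table section 4, on changes in HIV-RNA load and CD4, instead splits patients by use of concomitant CYP3A inhibitors.

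**The concern.** A set of strata should place every known value in exactly one row. Here one row ends at 4 years and the next begins at 5. A programmer who follows the text has nowhere to put a known duration between them. Anyone who fills the gap must choose a convention that the SAP does not give.

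The CYP3A problem is of a similar kind. Inducers and inhibitors are different drug groups, so the two terms pick out different patients. A programmer could use the defined inducer list or put together an inhibitor group that the SAP text does not define.

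Protocol section 8.2 plans to examine, by background characteristic, the factors that affect adverse drug reactions and efficacy. At stake is whether the duration rows and the CYP3A efficacy curves can be produced in one unambiguous way.

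**Working it through.** **Duration**

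Inputs: 1 year = 365 days (Date unit) and the printed row limits (Duration of disease). The SAP gives no figure of its own to reproduce.

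Years = days / 365.
- Upper end of the fourth row: 4 × 365 = 1,460 days.
- Start of the last numeric row: 5 × 365 = 1,825 days.
- Day-values between them: 1,461 to 1,824, that is 1,825 − 1,460 − 1 = 364.

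Where those 364 values go depends on how years are expressed before classing:

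| Reading | Row >3 to ≤4 (days) | Row ≥5 starts (day) | Placement of days 1,461–1,824 |
|---|---|---|---|
| Exact decimal | 1,096–1,460 | 1,825 | 364 in no row |
| Two decimals | 1,097–1,461 | 1,824 | 362 in no row (1,462–1,823), 1 in each neighbouring row |
| One decimal | 1,114–1,478 | 1,807 | 328 in no row (1,479–1,806), 18 in each neighbouring row |
| Completed years | 1,460–1,824 | 1,825 | 364 in >3 to ≤4 |
| Nearest year | 1,278–1,642 | 1,643 | 182 in >3 to ≤4, 182 in ≥5 |
| Rounded up | 1,096–1,460 | 1,461 | 364 in ≥5 |

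The gap exists on every decimal reading and on no whole-year reading. The whole-year readings disagree with each other about the same patients.

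Check of the repair: if the last row reads >4 years, every day-value falls in exactly one row on the exact decimal reading. On any whole-year reading, >4 and ≥5 are the same set, so nobody moves.

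Comparison within the SAP: the administration-period and total-dose strata use the same >a to ≤b form and close directly after the preceding row (>730 days after ≤730; >1,460 tablets after ≤1,460). They leave no gap.

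**CYP3A**

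No arithmetic applies beyond counting mentions in the SAP text:
- CYP3A inducer(s): five in the Handling of items entry, one in the composition table and one in the incidence table, 5 + 1 + 1 = 7.
- CYP3A inhibitors: one, in the HIV-RNA/CD4 entry.

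The supplied text has no definition of the inhibitor group and no reference to a list for it.

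**The case against.** **Durations may be meant as whole years.** This would close the gap, and rounding up would give sensible rows. But the SAP states no such rule. Its display rule keeps decimals, although a display rule does not settle how values are classed. Completed years would also stretch the ≤1 row to day 729 (2 × 365 − 1). The objection shows that the intent is uncertain, not that the text is complete.

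**Both may be translation or typing slips.** This is plausible: untranslated characters remain in nearby strata, and the inpatient/outpatient strata repeat a category. A slip still needs correcting, because the tables are built from this text.

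**The mock-ups and drug-list sheets were not supplied.** An inhibitor list could exist there. This stands as a limit: one can say only that the SAP text cites none.

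**The effect is small.** This also stands. The 364 days are the width of the gap, not a count of patients. A shortfall in the row total would be easy to notice.

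A reader might infer more than the documents support:
- *Patients lost from the safety analysis.* No; they lose a row for one background item only.
- *Inhibitors simply misprinted for inducers.* The documents do not show which was meant.
- *Inhibitors mentioned nowhere else in the SAP.* The list of concomitant anti-HIV drug types names several inhibitor classes; only CYP3A inhibitors appear once.
- *Mean-daily-dose strata that drop the extreme patients.* The note closing Handling of items explains that minimum and maximum stand for the displayed extremes.
- *Decade-only age coding as a similar error.* The SAP leaves its wider use unstated, which is missing detail and not a rule that misplaces anyone.

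**Conclusion.** Both parts hold as errors in the written specification, with a narrow effect.

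On the text as it stands, known durations over 4 and under 5 years have no row: 364 day-values on exact decimals, 362 on two decimals. They cannot properly be shown as unknown. Such patients would be missing from the duration rows in three outputs. They would also be missing from any test on the item, although the exclusion rule for tests does not cover them. This rests on 365-day years, which the SAP states, and on decimal classing, which it neither states nor rules out. The number of patients affected is not given and could be zero.

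The CYP3A efficacy split names a group other than the one the SAP defines and tabulates, and the group cannot be built from the supplied text. The number of patients in either group is not given.

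Overall adverse-reaction incidence, the other background items, and the HIV-RNA/CD4 results for all efficacy patients are unaffected. The HIV-RNA/CD4 output is not split by duration, so the gap does not reach efficacy.

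**What to change.** 1. In the duration-of-disease strata, change the last numeric row to >4 years. State whether durations are classed as decimal or whole years and, if whole, how they are rounded.
2. Reconcile the HIV-RNA/CD4 entry in table section 4 with the CYP3A item in Handling of items and with the two tables that display inducer use. State which CYP3A group the split uses and cite its drug list.

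The cost is SAP wording and minor programming, with no new data. If inhibitors are meant, a list of them must be cited or prepared.

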DRUG USE INVESTIGATION FOR HIV INFECTION PATIENTS OF MARAVIROC

- HRD Joint Survey -

NON-INTERVENTIONAL (NI) STUDY PROTOCOL

Drug Use-results Survey of Celsentri Tablets 150 mg – HRD Cooperative investigation – Protocol

1. Objectives

To understand the following matters and to examine whether or not a special drug use-results survey and/or postmarketing clinical study is needed:

- Unknown adverse drug reactions (ADRs)
- Occurrence of ADRs under actual conditions of use
- Factors that are likely to affect safety, efficacy and other relevant matters

In addition, effects on immune competence, liver function and the cardiovascular system will be also evaluated as priority investigation items.

2. Planned Sample Size of the Survey and Rationale of Determination

Based on an approval condition, the drug use-results survey of Celsentri will be conducted in all patients treated with this drug at survey sites to the extent possible.

For the drug use-results survey implemented as part of the HRD cooperative investigation in which Celsentri is included, however, consideration will be paid by setting the upper limit of the number of patients to be enrolled at sites where there are many survey subjects for eliminating the influence of the present survey on routine medical practice at the sites and maintaining the quality of the survey due to this acute increase in the number of patients. When paying consideration, approximately 40 patients per investigator should be enrolled in the HRD cooperative investigation while taking account of time points for collecting case report forms (CRFs) and for case review by the investigator. If it is necessary of select subjects from all patients, consideration should be given so that there is no arbitrarily bias in efficacy or safety.

3. Subjects

The indication of Celsentri is as follows:

CCR5-tropic HIV-1 infection

The subjects of this survey will be patients who are prescribed with Celsentri (including retrospective patients).

4. Planned Number of Survey Sites by Medical Department

Institutions with which many physicians with a lot of experience in treatment are affiliated and which have many target patients (27 sites; Appendix 1).

5. Methods

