Complications	Use the complications provided in the CRF at the first administration of CELSENTRI Tablets. The events that occurred and did not recover before the first administration of CELSENTRI Tablets in the 'adverse event' column. [Stratification] Absence, Presence, Unknown/not provided
Type of complications	Complications provided in the CRF at the first administration of CELSENTRI Tablets <Multiple-answers are acceptable in this column> In addition, reflect the ViiV Healthcare K.K.'s instruction for data amendment. [Stratification] • "Haemophilia": complications are present "1. Haemophilia"

	
•"Liver disorder": the disease selected as liver disorder in 'complication is present': 3. Hepatitis A", "4. Hepatitis B", "5. Hepatitis C", "6. Other liver disorders", or "8. Others"

The mean daily dose	
The mean dose for "administration period" Even if "administration period" is unknown, the provided value should be regarded as the mean when there is no change in "the dose". [Stratification] >minimum and < 2 tablets, 2 tablets, >2 tablets and <maximum, unknown/not provided

Dosing frequency	
Calculate the number of dosing in a day. [Stratification] 1, 2, ≥3 and ≤maximum, unknown/not provided

Administration period	
\sum (final administration date - first administration date+1). Exclude the washout period. [Stratification] ≤180 days, >180 and ≤365 日、 >365 and ≤730 日、 >730, unknown/not provided

Administration period <cumulative>	
Count "the number of patients" by accumulating "administration period", count "the number of patients with adverse reactions" based on the "administration period" until the first adverse reaction occurred, and count "the number of adverse reactions" based on the "administration period" until the applicable adverse reaction occurred. Exclude the washout period. [Stratification] ≤180 days, >180 and ≤365 日、 >365 and ≤730 日、 >730, unknown/not provided

Total dose	
\sum {(Final administration date - First administration date+1) × a daily dose}. Exclude the washout period.[Stratification]≤360 tablets, >360 tablets and ≤730 tablets, >730 tablets and ≤1460 tablets, >1460 tablets, unknown/not provided

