Tropism classification at the first administration of CELSENTRI Tablets.	Display the value obtained on the closest date to the first administration date of CELSENTRI Tablets within 30 days before/after the first administration. Display the earlier value obtained for this if the same values are found on the same dates both before and after the first administration. [Stratification] R5, X4, DM, NR, Not implemented* *If it was not conducted, separately record the reason for this (Prepare a list of the reasons why the tropism assay was not conducted).
Presence/absence of concomitant treatment	If any concomitant treatment was given in the “administration period” of CELSENTRI Tablets (for ≥1 day), select “present”. [Stratification] Absence, Presence, Unknown/not provided
Presence/absence of blood coagulation factor	Count the presence/absence of drugs administered while the patient was on CELSENTRI Tablets 150 mg (the drugs with the concomitant drug codes {6343406, 6343409, 6343429, 6343430, 6343414, 6343431, 6343432, 6343434} on the top). In addition, display the presence/absence when “present” was selected for the presence/absence of haemophilia. [Stratification] Absence, Presence, Unknown/not provided

*When the minimum/maximum are specified in the stratification of the mock-up, display the minimum/maximum of each item.

<<Handling of cases>>

Patients whose survey form was collected	On March 26, 2018, the data on all the patients registered during this survey period were locked. Therefore, they are the patients whose survey form was collected as of March 26, 2018.
Patients in the safety analysis group	
Patients excluded from the patients applicable to the following [Exclusion criteria from the safety analysis group] (Note that the patients with adverse reactions are not excluded).
 
[Exclusion criteria from the safety analysis group]
 
[1] Not visited after the first visit ⇒Patients whose survey form is composed of 1 volume alone, with “Outcome of patient” of “1. Not visited” or “2. Transferred”, and also with their first administration of CELSENTRI Tablets = the outcome confirmation date in “Outcome of patient”.
 
[2] Not administered ⇒Patients whose administration of CELSENTRI Tablets cannot be traced since the approval date (=December 25, 2008).
 
[3] Unable to re-survey adverse events ⇒ “8 Unknown” and “0. Not provided” for the presence/absence of adverse events”

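### As written, the SAP's mean-daily-dose strata omit their own end points, so a known dose at the observed minimum (if below 2 tablets) or maximum (if above 2) fits no stratum

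*SAP*

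**What the plan says.** In the SAP, Handling of items, the mean daily dose is the mean over the administration period. Where the dose did not change, the recorded value is used even if the period is unknown. Its strata are ">minimum and < 2 tablets, 2 tablets, >2 tablets and <maximum, unknown/not provided".

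The next item, dosing frequency, has the strata "1, 2, ≥3 and ≤maximum, unknown/not provided".

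Two further statements fix what minimum and maximum mean:

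- The footnote that closes Handling of items: "When the minimum/maximum are specified in the stratification of the mock-up, display the minimum/maximum of each item".
- The entries for the patient composition ratio and for ADR incidence per patient background, both under Type of Tables: "Calculate the minimum and the maximum for age, duration of disease, the mean daily dose, administration period, total dose".

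The ADR entry opens with "Prepare a table of incidence of adverse reactions on the following patient-background items", lists the mean daily dose among those items, and sends the programmer back to the definitions: "Follow the above <<Handling of Items>> for the definitions of each item per background". The composition table does the same. The list of ADR and infection onset status by background also includes the item.

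For hypothesis tests, General Definitions (Test) says: "Exclude “unknown”, “not provided” and “not assessable” from test".

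**The concern.** Strata for a tabulation should place every patient with a known value in exactly one row. Here the outer rows are bounded by values taken from the data, and the signs shut out the patients who supply those values. The dose is recorded, so the unknown row is not available to them either.

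Protocol section 8.2(1) names ADR incidence as a primary safety item and plans to look for factors affecting ADR onset by tabulating incidence against patient factors. In the dose breakdown, the patients on the lowest and highest mean dose carry the most contrast. A table built literally would leave them out, and its row counts would not add up to its total.

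**Working it through.** The documents contain no figure to reproduce. The question is whether the strata cover every known dose.

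**Step 1: what the bounds are.** The footnote and the two table entries show that minimum and maximum are the observed extremes of the item. They are not outside limits such as 0 or a ceiling that no patient reaches. By definition, at least one patient lies on each.

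**Step 2: coverage.** Write m for the observed minimum, M for the observed maximum, and x for a patient's mean daily dose in tablets. As written, the strata for known doses are m < x < 2, x = 2, and 2 < x < M.

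- If m < 2, then x = m fails the first stratum and is in neither of the others.
- If M > 2, then x = M fails the third stratum and is in neither of the others.
- If an extreme equals exactly 2, it falls in the middle stratum and that end has no gap.

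The number unclassified is therefore

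U = n(x = m) × [m < 2] + n(x = M) × [M > 2],

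where each square bracket is 1 if the condition holds and 0 otherwise. If m < 2 and M > 2, U is at least 1 + 1 = 2.

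**Step 3: illustration.** The dose distribution is not in the documents. The sets below are invented, with 100 patients each, and only show how the rule behaves.

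| Assumed doses (patients at tablets/day) | Strict: below 2 / 2 / above 2 | In no stratum | Inclusive: below 2 / 2 / above 2 |
|---|---|---|---|
| A: 5 at 1, 2 at 1.5, 30 at 2, 3 at 3, 50 at 4, 10 at 8 | 2 / 30 / 53 | 5 + 10 = 15 | 7 / 30 / 63 |
| B: 10 at 1, 30 at 2, 60 at 4 | 0 / 30 / 0 | 10 + 60 = 70 | 10 / 30 / 60 |
| C: 40 at 2, 60 at 4 | 0 / 40 / 0 | 60 | 0 / 40 / 60 |
| D: 10 at 1, 90 at 2 | 0 / 90 / 0 | 10 | 10 / 90 / 0 |
| E: 100 at 2 | 0 / 100 / 0 | 0 | 0 / 100 / 0 |

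With strict bounds, 0 to 70 of 100 are unclassified in these sets. In B, C and D only one stratum is left populated, so no comparison across dose is possible. With inclusive bounds, none is unclassified in any set.

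**Step 4: does another rule catch these patients?** The test rule removes unknown, missing and non-assessable values. A known extreme dose is none of these, and no other rule assigns it to a row.

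**Step 5: neighbouring items.** Dosing frequency closes its top stratum with ≤ at the maximum. Administration period and total dose have open-ended outer strata (up to 180 days and over 730; up to 360 tablets and over 1460), so no extreme value can fall outside. Mean daily dose is the only item with strict signs at data-derived extremes.

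**The case against.** The best defence is that minimum and maximum serve as display labels. The footnote is about displaying them, and the natural intent is three rows (below 2, exactly 2, above 2) with the observed range printed in the row heading. A heading that prints the minimum while excluding the patients who define it defeats itself, and nothing in the SAP suggests that known doses should be left out. The English text also shows signs of imperfect translation: Japanese characters remain in the administration-period strata, and the inpatient/outpatient strata list inpatient twice. The table shell is not available, and the SAP closes by saying that table forms may change. A programmer may well use inclusive bounds without comment.

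This is persuasive on intent and is why the point is minor. It does not remove the gap. Handling of items is the definition that the tables are told to follow, and a specification should not depend on the programmer departing from it.

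Two further objections also stand. First, ties should not be taken for granted. The item is a mean over the administration period, so a patient whose dose changed can have a fractional value, and an extreme may belong to one patient only. Ties are plausible among patients on a constant dose, but the documents do not show how many there are. Second, a reader might infer that the highest-exposure patients disappear from the safety evaluation. The documents do not support that. Nothing in the strata removes anyone from the safety analysis set, the overall ADR incidence or the adverse reaction tables, and total dose remains as a separate exposure breakdown with open ends.

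**Conclusion.** The point holds as a wording error in an operative stratification rule. As written, a known mean daily dose at the observed minimum (if below 2) or the observed maximum (if above 2) has no stratum. The size is at least one patient at each such end plus any ties, and zero at an end where the extreme is exactly 2. This rests on reading minimum and maximum as observed values, which the footnote and the table entries support.

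The effect is limited to the mean-daily-dose rows of the composition and ADR-by-background tables and to any test on those rows. It is also visible, because the row counts would fall short of the total.

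A reader might go further and put a percentage on the loss, or conclude that extreme doses were left out on purpose. Neither is supported. The documents give no dose distribution, so the illustrative counts are not estimates, and the inclusive sign in the dosing-frequency row points to a slip.

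**What to change.** Change two symbols in the SAP and the table shell, so that the strata read: ≥minimum and <2 tablets; 2 tablets; >2 tablets and ≤maximum; unknown/not provided. Every known dose then falls in exactly one stratum.

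Add a programming check that the dose-stratum counts, including the unknown row, add up to each table's own total: patients with a collected survey form for the composition table, and the safety analysis set for the ADR tables. If tables have already been produced, the same sum shows whether inclusive bounds were used in practice.

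The change needs no new data and touches no dose or clinical rule. The cost is a one-line edit and, at most, a rerun of the affected rows.
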